### **10.6 Unanticipated Serious Adverse Device Effects**

An unanticipated serious adverse device effect (USADE) is any device-related SAE that meets one or more of the following criteria:

- Is not identified in nature, severity, or frequency in current literature on the product
- Is life-threatening, even if temporary in nature
- Results in permanent impairment of a body function or permanent damage to a body structure

- Necessitates medical or surgical intervention to preclude permanent impairment of a body function or permanent damage to a body structure

Also considered an USADE is any device malfunction that would be likely to cause or contribute to a death or serious injury if the malfunction were to recur. The investigator will notify the sponsor within 24 hours of any device malfunction and a representative will provide instruction for the return of any faulty syringe for evaluation.

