## 10.7.2 Relationship to Study Product

A determination will be made, by the investigator, of the relationship, if any, between an AE and any study product, anesthesia employed, the study device, or the injection procedure, as applicable, using the guidelines presented in **Table 10.2**.

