**Study Devices:**

[figure not shown]
- JUVÉDERM® VOLITE® is a sterile non-pyrogenic physiological solution of cross-linked hyaluronic acid which is not of animal origin. It consists of cross-linked HA produced by *Streptococcus* of bacteria, formulated to a concentration of 12 mg/mL and 0.3% w/w lidocaine, HCl, in a phosphate buffer.
- JUVÉDERM® VOLBELLA® with Lidocaine injectable gel is a sterile, biodegradable, non-pyrogenic, viscoelastic, clear, colorless, homogeneous gel implant. It consists of cross-linked HA produced by *Streptococcus* of bacteria, formulated to a concentration of 15 mg/mL and 0.3% w/w lidocaine, HCl, in a phosphate buffer.
- JUVÉDERM® VOLIFT® with Lidocaine is a sterile non-pyrogenic physiological solution of cross-linked hyaluronic acid which is not of animal origin. It consists of cross-linked HA produced by *Streptococcus* of bacteria, formulated to a concentration of 17.5 mg/mL and 0.3% w/w lidocaine, HCl, in a phosphate buffer.
- JUVÉDERM® VOLUMA® with Lidocaine is a sterile, biodegradable, non-pyrogenic, viscoelastic, clear, colorless, homogenized, HA gel implant (dermal filler). It consists of crosslinked HA formulated to a concentration of 20 mg/ml, suspended in a physiological buffer. The HA is mixed with phosphate buffer and 0.3% lidocaine, HCl, and crosslinked by adding BDDE to form a 3-dimensional HA gel.
- JUVÉDERM® VOLUX® with Lidocaine is a sterile, pyrogenic physiological solution of cross-linked hyaluronic acid that is not of animal origin. It consists of crosslinked HA gel 25 mg and 3 mg lidocaine, HCl, in a phosphate buffer.
- HArmonyCa Lidocaine™ is a dermal filler consisting of synthetic calcium hydroxyapatite microspheres, formulated to a concentration of 55.7% (w/w), embedded in a cross-linked sodium hyaluronate gel (0.886% [w/w] HA) from a non-animal source with 0.3% (w/v) lidocaine HCl.

[figure not shown]

[figure not shown]

[figure not shown]

[figure not shown]

[figure not shown]

[figure not shown]

[figure not shown]

[figure not shown]

[figure not shown]

[figure not shown]

[figure not shown]

[figure not shown]

[figure not shown]

[figure not shown]

[figure not shown]

[figure not shown]

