9.2 Adverse Events

Adverse events (AEs) will be summarized and presented using primary MedDRA System Organ Classes (SOCs) and preferred terms (PTs).

An AE will be considered a JUVÉDERM injection related AE if it has a reasonable possibility (Possible, Probable, or Causal relationship) that the JUVÉDERM injections caused the event. The JUVÉDERM injections include JUVÉDERM VOLITE, JUVÉDERM VOLBELLA, JUVÉDERM VOLIFT, JUVÉDERM VOLUMA, and JUVÉDERM VOLUX.

An AE will be considered a BOTOX related AE if it has a reasonable possibility (Reasonable Possibility) that the BOTOX cosmetic caused the event.

An AE will be considered a study procedure related AE if it has a reasonable possibility (Possible, Probable, or Causal relationship) that the study procedure caused the event.

An AE will be considered a device related AE if it is related to a device malfunction/deficiency.

If the causal relationship to the study treatment/device/procedure is missing for an AE that occurred on or after the date of the first study treatment, then a causal relationship will be imputed for analysis. The imputed values for relationship to study treatment/device/procedure will be used for the incidence summary; the actual values will be presented in data listings.

If severity is missing for an AE that occurred before the date of first study treatment, then a severity of mild will be imputed for analysis. If the severity is missing for an AE that occurred on or after the date of the first study treatment, then a severity of severe will be imputed. The imputed values for severity will be used for the incidence summary; the actual values will be presented in data listings.

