9.2.2 Adverse Event Overview

Overall summaries of TEAEs will include:

- The number and percentage of subjects with any TEAE
- The number and percentage of subjects with any TESAE
- The number and percentage of subjects with any severe TEAE
- The number and percentage of subjects with any TEAE related to JUVÉDERM VOLITE
- The number and percentage of subjects with any TEAE related to JUVÉDERM VOLBELLA
- The number and percentage of subjects with any TEAE related to JUVÉDERM VOLIFT
- The number and percentage of subjects with any TEAE related to JUVÉDERM VOLUMA
- The number and percentage of subjects with any TEAE related to JUVÉDERM VOLUX
- The number and percentage of subjects with any TEAE related to BOTOX cosmetic
- The number and percentage of subjects with any TEAE related to study procedure
- The number and percentage of subjects with any TEAE related to device
- The number and percentage of subjects with any TEAE leading to study discontinuation

- The number and percentage of subjects with any TEAE leading to death
- The number and percentage of subjects with any TESAE related to JUVÉDERM VOLITE
- The number and percentage of subjects with any TESAE related to JUVÉDERM VOLBELLA
- The number and percentage of subjects with any TESAE related to JUVÉDERM VOLIFT
- The number and percentage of subjects with any TESAE related to JUVÉDERM VOLUMA
- The number and percentage of subjects with any TESAE related to JUVÉDERM VOLUX
- The number and percentage of subjects with any TESAE related to BOTOX cosmetic
- The number and percentage of subjects with any TESAE related to study procedure
- The number and percentage of subjects with any TESAE related to device
- The number and percentage of subjects with any TESAE leading to study discontinuation
- The number and percentage of subjects with any TESAE leading to death
 - Before BOTOX Treatment
 - On or After BOTOX Treatment

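### SAP 9.2 ties device-related AEs to malfunction or deficiency, which makes the device count too low for all six fillers and leaves HArmonyCa-caused events in no product- or device-related table

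*SAP*

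**What the plan says.** SAP 9.2 sets out how an AE is classed as related. For Juvéderm injections, BOTOX and the study procedure the test is a reasonable possibility of causation. For devices the test is different: "An AE will be considered a device related AE if it is related to a device malfunction/deficiency". No other device criterion is given.

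This rule feeds two rows of the SAP's Adverse Event Overview: "The number and percentage of subjects with any TEAE related to device" and "The number and percentage of subjects with any TESAE related to device". It also feeds the device tables by SOC and PT for TEAEs (with a version by maximum severity) and for TESAEs.

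Protocol Appendix 8 separates the study drug (BOTOX) from a list headed "Study Devices". That list holds five Juvéderm products and HArmonyCa, which "is a dermal filler consisting of synthetic calcium hydroxyapatite microspheres".

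Protocol 10.6 says a USADE "is any device-related SAE that meets one or more of the following criteria", and then adds a second route: "Also considered an USADE is any device malfunction that would be likely to cause or contribute to a death or serious injury". Protocol 10.7.2 has the investigator judge "the relationship, if any, between an AE and any study product, anesthesia employed, the study device, or the injection procedure". Protocol 11.5 plans to summarize TEAEs by relationship to drugs, devices and procedures.

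**The concern.** The fillers are the devices, so a reader would expect a device-related table to hold events that a filler caused. Under the SAP rule, an event caused by a filler that worked as intended does not qualify. The protocol does not make malfunction a condition of device relatedness. The SAP says in its Introduction that changes to protocol-planned analyses are set out in Appendix C, but this one is not there.

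What is at stake is attribution of harm. If another table attributes the event to the product, the problem is one of labelling and counting. If no other table does, the report cannot show how many subjects had events attributed to that product.

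**Working it through.** No alpha, power or rate enters this point. It is checked by tracing each device through the SAP's rules and tables.

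**Inputs.** The device list comes from protocol Appendix 8. The causality rules come from SAP 9.2. The rows come from the SAP's Adverse Event Overview. The SOC/PT tables come from the two SAP sections that follow the overview, one on TEAEs by SOC, PT and severity, the other on SAEs and discontinuations (their numbers repeat 9.2.1 and 9.2.2).

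**Step 1: where can an event caused by a correctly working filler appear?**

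| Study device | Causality rule in SAP 9.2 | Own related TEAE and TESAE rows | Named in the study-treatment SOC/PT tables | Meets the device criterion without malfunction or deficiency |
|---|---|---|---|---|
| Each of the five Juvéderm fillers | Yes, reasonable possibility | Yes | Yes | No |
| HArmonyCa | None | No | No | No |

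**Step 2: count.** There are 5 + 1 = 6 study devices.
- Covered by the device-related tables for events without malfunction or deficiency: 0 of 6.
- Covered by product-related tables: 5 of 6.
- Covered by neither: 6 − 5 = 1 of 6, namely HArmonyCa.

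**Step 3: does the protocol require malfunction?**
- Protocol 10.2 defines a device AE through use of the device, with no reference to malfunction.
- Protocol 10.6 has device-related serious events and malfunctions as two routes to a USADE. If device-related already meant malfunction-related, the first route would add little.
- Protocol 11.5 plans summaries by relationship to devices, with no malfunction condition.

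**Step 4: is the narrow row needed to report deficiencies?** No. SAP 9.8 already summarizes subjects with device deficiencies by suspect device type.

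**Step 5: what remains for HArmonyCa?** Its events enter the all-TEAE tables, and the procedure-related tables if the investigator attributes them to the procedure. Local reactions recorded in the diary are summarized under SAP 9.5. None of these shows which events were attributed to the product.

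**The case against.** The strongest reply is that SAP 9.2 already has a causality rule for the Juvéderm products that needs no malfunction, and that each of the five has its own TEAE and TESAE rows and a place in the treatment-related tables. This is right. A reader might infer that filler harm disappears from the report, or that a low device row would pass as evidence that the fillers are harmless. The documents do not support either inference for these five products: their related events sit in separate rows above the device row.

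A reader might also infer that the SAP tables could not be reconciled with USADE reporting. That goes too far. Protocol 10.5.2 makes USADE classification a written sponsor evaluation, protocol 11.5 asks for no USADE table, and the SAP lists all AEs, so serious events among about 60 subjects can be traced one by one. A USADE count is optional.

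Some points of wording also stand. Protocol 10.6 uses the term device-related without defining it, and 10.7.2 names study product and study device as separate items, so neither section alone settles the label. The SAP says if rather than only if, and leaves deficiency undefined. Missing relationships are imputed as causal, so a few events without a malfunction could enter the device tables. Even so, malfunction or deficiency is the only criterion the SAP states.

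For HArmonyCa, one could add that SAP 9.1 presents safety by treatment group, so all TEAEs are shown for subjects with and without HArmonyCa. That contrast is not randomized, and both groups are due to receive Juvéderm and BOTOX as well. It does not replace the investigator's attribution. The reply therefore does not reach HArmonyCa.

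**Conclusion.** The point holds, with a different size for the two kinds of filler. For the five Juvéderm fillers, the related-to-device count is mislabelled and too low, but the events are counted elsewhere. For HArmonyCa, events caused by a correctly working product reach no product- or device-related table. That is more than a label: adding HArmonyCa was the stated reason for protocol Version 2.

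The number of subjects affected cannot be derived, because the documents give no event rates. No efficacy result changes. The conclusion rests on reading the SAP's single device criterion as exclusive and on Appendix 8 as the list of study devices.

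**What to change.** In SAP 9.2, define a device-related AE as one with a reasonable possibility of causation by any of the six fillers, naming HArmonyCa. State how the protocol Table 10.2 categories (Highly Probable, Probable, Possible, Not Related) map to the SAP's Possible, Probable and Causal, because the two scales differ.

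Add HArmonyCa-related TEAE and TESAE rows to the overview, and include HArmonyCa in the study-treatment tables by SOC and PT. Keep the present device row, but relabel it as related to device malfunction or deficiency. Record the definition in Appendix C. A USADE row may be added if wanted.

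The cost is SAP wording and a few extra table rows. This assumes that the relationship to HArmonyCa was captured, as protocol 10.7.2 requires for any study product. The eCRF is not among the documents, so this should be confirmed first.

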### 5.1 Inclusion Criteria

The following are requirements for entry into the study.

1. 35 to 65 years of age, inclusive, at screening (male or female)
2. Accept the obligation not to receive any other facial procedures or treatments at any time during the study that are not related to the study
3. Women of childbearing potential must have a negative urine pregnancy test before each injectable treatment and practice a reliable method of contraception throughout the study
4. Willing to avoid direct and prolonged sun exposure to the facial skin, which includes tanning beds, for the duration of the study
5. Must qualify to receive BOTOX treatments, in at least one area, as per the approved Product Monograph including treatment of hyperkinetic lines for the glabellar, crow's feet, and forehead lines:
  - Glabellar injection: glabellar rhytides characterized as 2 (moderate) or 3 (severe) during maximum muscle contraction on the evaluation of the facial wrinkle scale (FWS)
  - CFLs characterized as 2 (moderate) or 3 (severe) during maximum smile on the evaluation of the FWS
  - FHLs of 2 (moderate) to 3 (severe) rating at maximum eyebrow elevation as assessed using the FWS
6. Must qualify to receive Juvéderm dermal filler treatments as per the approved Directions for Use. Subjects must use at least two different Juvéderm filler products in at least two different aesthetic anatomic areas. A summary of inclusion criteria by facial area for potential subjects for filler treatments is presented in [Table 5.1](#).

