2.2 Study Design Overview

This Phase 4 study is a prospective, interventional, multicenter, combination medical device and drug post marketing study. Each subject will be in the study for up to approximately 5 months and act as his/her own control. All products will be used as per their license only. The investigators will perform all treatments and evaluations.

The study is planned to enroll 60 subjects consecutively at approximately 7 study sites in Brazil. Recruitment will also target men, who are typically under-represented in aesthetic studies.

All subjects will sign an informed consent form (ICF) and begin the study at the screening visit (V0). Subjects following screening (V0) will enter the study and receive an initial treatment of HArmonyCa Lidocaine at Visit 1 (V1), followed by Juvéderm fillers at Visit 3 (V3), and BOTOX at Visit 5 (V5) as indicated in the study design diagram ([Figure 1](#)). If the decision is made to not treat with HArmonyCa Lidocaine, the subject may begin with Juvéderm fillers at V1. As indicated in the diagram, touch-ups of HArmonyCa at Visit 2 (V2), Juvéderm at Visit 5 (V5), and BOTOX at Visit 6 (V6) are optional. If a touch-up of HArmonyCa (V2) is not performed, the subject may advance in the study timeline to the next study visit procedures. If a touch-up of BOTOX is not performed, the subject will return on schedule for Visit 7 (V7). A

subject not receiving Juvéderm touch-up would continue with BOTOX treatment (and all study procedures) outlined for V5. To reduce the number of subject visits, V0 can be combined with the initial treatment visit (V1), if judged by the investigator to be appropriate and acceptable for the subject. End of study is the last clinical visit an enrolled subject has in this study, V7 (after approximately 5 months of treatment). Subjects who discontinue prematurely will be asked to return for the last clinical visit for end-of-study data collection. Identical study procedures will not be repeated where the visits are combined. The schedule of activities is shown in [Table 1](#).

Figure 1. Study Design

[figure not shown]

Table 2. Schedule of Activities (SOA)

Study Visit	V0 ¹	V1	V2	V3	V4	V5	V6 ²	V7 ³
Visit window	Screening	Day 1	Day 30	Day 60	Day 90	Day 120	Day 135	Day 150
	(Day -14 to Day -1)	N/A	(30 ± 7 days after V1)	(30 ± 7 days after V2)	(30 ± 7 days after V3)	(30 ± 7 days after V4)	(15 ± 7 days after V5)	(15 ± 7 days after V6)
STUDY TREATMENTS								

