8.0 Efficacy Analyses

8.1 General Considerations

- All efficacy analyses will be conducted in the Evaluable Population.
- Day 1 is defined as the day on which the study treatment is first received.
- Baseline for efficacy is defined as the last non-missing assessment on or prior to Day 1.
- Study day is relative to Day 1.
- Change from baseline will be computed as post-baseline minus baseline.

- Categorical variables will be summarized descriptively using number of subjects with observed values or events (n) and the percentage of subjects with observed values or events.
- Continuous variables will be summarized descriptively using number of subjects with observed values (n), mean, standard deviation (SD), standard error of mean (SEM), median, minimum (min), and maximum (max).
- Unless otherwise specified, the estimated mean and median for a set of values will be printed out to 1 more significant digit than the original values; the SD and SEM will be printed out to 2 more significant digits than the original values; the min and max will report the same significant digits as the original values.
- Shapiro-Wilks test will be used to check the normality assumption. If the normality assumption is met, the statistical hypothesis test will be performed based on one-sample, one-sided t-test at 0.025 significance level. If the normality assumption is not met, Wilcoxon signed-rank test will be used instead and a 97.5% confidence interval (CI) for the median will be presented using the Hodges Lehmann method. Shapiro-Wilks and Wilcoxon signed-rank test will be performed by proc univariate procedure, and Hodges Lehmann CI of the median for paired samples will be performed based on a SAS macro by Han (2008) [\[1\]](#) as specified in SPP Section 3.3.
- All CIs will be 1-sided 97.5% CIs, and will be printed to 2 decimal places, unless stated otherwise. P-values output will be in the format: ‘0.xxxx’, where xxxx is the value rounded to 4 decimal places. Every p-value less than 0.0001 will be presented as <0.0001. If the p-value is returned as >0.9999, then present it as it is.
- Unless otherwise specified, the summaries will be provided by treatment group, gender, and overall.

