9.2.1 Treatment-Emergent Adverse Events

Treatment-emergent adverse event (TEAE) is defined as any AE with the onset on or after the date (and time, if known) of the first study treatment. A TEAE will be considered a treatment-

emergent serious adverse event (TESAE) if it is a TEAE that additionally meets any SAE criterion.

All AEs will be included in a listing. Only TEAEs will be included for summaries, unless otherwise specified. Subjects with any TEAEs, TESAEs, severe TEAEs, TEAEs related to study treatment, TEAEs related to study procedure, TEAES related to device, TEAEs leading to study discontinuation, TEAEs leading to death, TESAEs related to study treatment, TESAEs related to study procedure, TESAEs related to device, TESAEs leading to study discontinuation, and TESAEs leading to death will be summarized.

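### Missing relatedness is imputed as causal from the first treatment of any kind, so an event with a blank rating could be attributed to a product the subject had not yet received, or never received

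*SAP*

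**What the plan says.** SAP 9.2 (Adverse Events) gives separate definitions of a related event for Juvéderm, for BOTOX and for study procedure. It then applies one imputation rule to all of them: if the relationship "is missing for an AE that occurred on or after the date of the first study treatment, then a causal relationship will be imputed". The imputed values "will be used for the incidence summary; the actual values will be presented in data listings".

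No other section narrows the date to a product. SAP 9.2.1 defines a treatment-emergent event as "any AE with the onset on or after the date (and time, if known) of the first study treatment". In the efficacy section, SAP 8.1 likewise states that "Day 1 is defined as the day on which the study treatment is first received".

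The results are nevertheless reported product by product. The overview in SAP 9.2.2 has separate rows for each of the five Juvéderm products and for BOTOX, for example "The number and percentage of subjects with any TEAE related to BOTOX cosmetic", with matching rows for serious events. The tables by system organ class and preferred term name the same six products.

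Treatment is staged. SAP 2.2 places HArmonyCa at V1, Juvéderm from V3 and BOTOX at V5. HArmonyCa is optional: "If the decision is made to not treat with HArmonyCa Lidocaine, the subject may begin with Juvéderm fillers at V1". On the choice of Juvéderm products, Protocol 5.1 states: "Subjects must use at least two different Juvéderm filler products in at least two different aesthetic anatomic areas". The Safety Population (SAP 4.1.3) requires receipt of only one product of any kind.

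**The concern.** A rule that treats a missing rating as related makes sense once the subject has been exposed to the product. Here the rule starts at the first injection of anything, while the tables it feeds are specific to a product. Between those two dates, and for products a subject never receives, the rule assigns a relationship that cannot exist.

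At stake are the product-specific counts of related adverse events and related serious adverse events. In a post-marketing study of combined treatment, readers will use those rows to see which product an event was attributed to.

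**Working it through.** The plan gives no figure for this rule. Its one computed figure, the sample size, reproduces: one-sample, one-sided t-test, alpha 0.025, mean change 12.0, SD 25.0 gives power 0.903 at n = 48, and 48/(1 − 0.20) = 60. Only the 60 is used below.

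**Step 1. Follow the rule for a single event.** These cases are constructed to show the logic; they are not data.

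- *Before BOTOX.* A subject on the full path has an event at V2 (nominal Day 30), and the BOTOX rating is blank. Onset is after first treatment, so the event is treatment-emergent and the relationship is imputed. The subject enters the BOTOX-related row. First BOTOX is at V5 (nominal Day 120), which is 120 − 30 = 90 days later.
- *Juvéderm product never given.* A subject receives VOLIFT and VOLUMA only, and the VOLUX rating of an event is blank. The subject enters the VOLUX-related row.
- *BOTOX never given.* A subject leaves after V4. One injected product is enough for the Safety Population, so a blank BOTOX rating puts this subject in the BOTOX-related row.

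**Step 2. Compare with Protocol Table 10.2.** All three related categories (Highly Probable, Probable, Possible) require onset a reasonable time after the product was given. None of the three cases can meet that. The category that fits is Not Related, which the table defines partly by timing. The SAP would therefore impute a rating that an investigator following the protocol could not give.

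**Step 3. Nominal time before first BOTOX.** Inputs are the visit intervals in Protocol Table 6.1: 30 ± 7 days between successive visits from V1 to V5, then nominally 15 + 15 days to V7. Footnotes 13 and 14 describe the two shorter paths.

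| Path | First treatment to first BOTOX (days) | First treatment to V7 (days) | Share | Range to first BOTOX with ± 7-day windows (days) |
|---|---|---|---|---|
| Full | 4 × 30 = 120 | 120 + 30 = 150 | 80% | 4 × 23 = 92 to 4 × 37 = 148 |
| No HArmonyCa touch-up | 3 × 30 = 90 | 90 + 30 = 120 | 75% | 69 to 111 |
| No HArmonyCa | 2 × 30 = 60 | 60 + 30 = 90 | 67% | 46 to 74 |

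Counting from the day labels instead, the full path gives 119/149 = 79.9%.

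**Step 4. Products never received.**

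- Juvéderm: at the eligibility minimum, 5 − 2 = 3 of the five product rows concern a product the subject did not get.
- BOTOX: if the whole planned drop-out of 20% occurred before V5, 0.20 × 60 = 12 subjects would never receive it. This is a ceiling under the plan's own assumption, because the 20% also covers incomplete questionnaires.

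**Step 5. What cannot be computed.** No rate of missing ratings is given, so the number of misattributed events is unknown. One affected subject among 60 moves a row by 1/60 = 1.7 percentage points, and two by 3.3. As an illustration by assumption only, suppose a share m of BOTOX ratings is blank and every subject has e events before BOTOX. The expected number of subjects wrongly counted is 60 × [1 − (1 − m)^e]. With m = 1% and e = 1 this is 0.6; with m = 5% and e = 3 it is 8.6; with m = 0 it is 0.

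**The case against.** **Imputing missing as related is conservative.** It errs toward over-reporting, and after exposure that is a sound convention. It does not justify an attribution known to be impossible.

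**There may be nothing to impute.** This stands as a limit on size. Protocol 10.7.2 asks for the relationship where applicable, and Table 10.2 already offers Not Related for an event with the wrong timing. The case report form may record a product not yet given as not applicable, and the separate programming plan may apply a date for each product. Neither is among the documents, and the SAP does not mention such handling. A reader might infer that blanks cluster where a product has not been given; nothing in the documents supports that.

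**The overview separates events before and after BOTOX.** SAP 9.2.2 ends with two such rows. In the text as available they sit under the last bullet only, which may be an artefact of the layout. Even if they apply to the whole table, they would display an anomalous event without stopping the imputation, and they do nothing for Juvéderm products not received. The listings do keep the actual values, so any imputed attribution can be traced.

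**Every subject is meant to receive every treatment.** SAP 2.3 says so, and BOTOX eligibility is required. By plan, then, subjects who never receive BOTOX are mainly early withdrawals, and three unreceived Juvéderm products is the extreme case, not the typical one.

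**Conclusion.** The point holds as a defect in a stated rule: the imputation has one start date and no exposure condition, while the tables it feeds are specific to a product. A blank rating could then be counted as related to BOTOX or a Juvéderm product that the subject had not received.

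A reader might go further and infer that the tables will contain false attributions, or that 80% of the BOTOX-related count is suspect. The documents support neither. The effect arises only where a rating is blank, the number of blanks may be zero, and the percentages in Step 3 are shares of nominal calendar time, not of events, subjects or bias.

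The effect is confined to descriptive safety tables for BOTOX and the individual Juvéderm products. HArmonyCa has no related-event definition in SAP 9.2 and no related-event row in the overview, so it is not involved here. The primary endpoint and the hypothesis tests are not affected. The conclusion assumes that the rule is programmed as written and that no unseen document adds an exposure condition.

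**What to change.** Amend SAP 9.2 so that, when the relationship to a product is missing:

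- a relationship is imputed only if onset is on or after the date (and time, if known) of that subject's first injection of that product;
- the imputed value is taken from that product's own scale, for example Reasonable Possibility for BOTOX, whose definition lists no causal level;
- if the product had not yet been given, or was never given, the relationship is set to not related or not applicable.

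The study-procedure rule can stay as it is. Moving its date back to the first study procedure would not change summaries that are limited to treatment-emergent events.

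The cost is a SAP amendment, as Protocol 11.8 requires for a change to planned analyses, and one date comparison per product in programming. SAP 6.0 already summarises injections by product and visit, so no new data and no protocol amendment are needed.
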